6.2.1 Demographic Summary

Descriptive statistics will be summarized for continuous demographics variables (e.g., age, weight, height, and BMI) and frequency counts will be tabulated for categorical demographics variables (e.g., gender, ethnicity, race, income level, and highest education grade level) by study group, and overall. The variable BMI is calculated from the weight and height collected at the Screening assessment and age is calculated from the date of the Screening visit.

The CSP, mITT and PP populations will be used for this summary.

6.2.2 Smoking History

CPD and years of smoking (calculated from Screening date reported at Screening will be listed. Descriptive statistics will be summarized by study group, age class, and gender for continuous variables and frequency counts will be tabulated for categorical variables.

The CSP, mITT and PP populations will be used for this summary.

6.2.3 Urine BOE and BOPH

Urine biomarker concentration (including each component of NE), urine creatinine concentration, and the creatinine-adjusted urine biomarker concentration will be listed by subject and study visit for urine NE, total NNAL, NNN, 11-dehydrothromboxane B₂, and 8-epi-prostaglandin F_{2a}. All BLQ values will be presented as “BLQ” in the listings.

Creatinine-adjusted urine biomarker concentration, absolute change from baseline creatinine-adjusted urine biomarker concentration, and percent change from baseline creatinine-adjusted urine biomarker concentration will be summarized by group and visit for each of the following biomarkers: urine NE, total NNAL, NNN, 11-dehydrothromboxane B₂, and 8-epi-prostaglandin F_{2a} using descriptive statistics (number of observations [n], number of missing values [n missing], arithmetic mean (mean), standard deviation [SD], coefficient of variation [CV%], standard error of the mean (SEM), minimum, median, minimum, maximum, and 95% CI). The descriptive statistics will be provided for both mITT and PP populations.

6.2.4 Blood BOE and BOPH

Blood biomarker concentrations will be listed by subject and study visit for WBC count, HDL-C, sICAM-1, and COHb. All BLQ values for COHb will be presented as “BLQ” in the listings.

Blood biomarker concentration, absolute change from baseline blood biomarker concentration, and percent change from baseline biomarker concentration will be summarized by group and study visit using descriptive statistics (number of observations[n], number of missing values [n missing], arithmetic mean [mean], standard deviation [SD], coefficient of variation [CV%], standard error of the mean [SEM], minimum, median, maximum, and 95% CI). BLOQ COHb saturation will be treated as one-half the lower limit of quantitation (LLOQ). The descriptive statistics will be provided for both mITT and PP populations.

6.2.5 Product Use and Compliance

Product Use

The number of cigarettes smoked per day, number of new e-vapor cartridges started per day, and number of puffs taken using test products (≤ 20 puffs or > 20 puffs) will be listed by subject and study day. Continuous variables will be summarized by descriptive statistics while categorical data will be presented using frequency count table. The average number of cigarettes smoked per day and e-cartridges started per day will be summarized by group and Week (Weeks 12 through 24) using descriptive statistics (number of observations [n], number of missing values [n missing], arithmetic mean [mean], standard deviation [SD], coefficient of variation [CV%], standard error of the mean [SEM], minimum, Q1, median, Q3, maximum and 95% CI). The overall average for Weeks 12 through 18 and Weeks 24 through 24 and Weeks 1 through 24 (CPD only for Weeks 1-24) will be presented. The percent change from Baseline to Week 18, Week 24, and Weeks 1-24 (CPD only for Weeks 1-24) will be calculated, where:

- Baseline for CPD is defined as the CPD reported at Screening, Visit 2 of the 12-week ALCS-RA-16-06-EV study;
- Baseline for the test products is defined as the average of Week 1 of the 12-week ALCS-RA-16-06-EV study;
- Week 18 is defined as the average of Week 18;
- Week 24 is defined as the average of Week 24;
- Weeks 1-24 is defined as the average of Weeks 1-24.

Frequency tables (n, %) will also be used to summarize the proportions of subjects in the following percent change categories: reduce, no change, or increase from Baseline to Week 24 for each study group.

Compliance

ECO concentration, creatinine-adjusted NNN concentration, and absolute and percent change from baseline in creatinine-adjusted NNN concentration will be listed by

subject and study day. Frequency tables (n and %) will be used to summarize eCO (≤ 5 , >5 to ≤ 8 and >8 ppm) and NNN (< 80% reduction from baseline or $\geq 80\%$ reduction from baseline) for assessment of compliance and noncompliance for each study group.

Analysis of NNN will be performed on the mITT population. Other product use and compliance variables will be summarized using available data.

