2. OBJECTIVES AND ENDPOINTS

2.1 Objectives

2.1.1 Primary Objective

The primary objective is to:

Compare absolute changes in selected biomarkers^a from Baseline^b to Week 24 (EOS) between adult smokers who continue to smoke conventional cigarettes (Control group) ad libitum and adult smokers who have completely^c switched to ad libitum use of test e-vapor products (Test groups) for 24 weeks.

^a Selected biomarkers include:

- o White Blood Cell Count (WBC Count)
- o High Density Lipoprotein Cholesterol (HDL-C)
- o Urinary 8-epi-prostaglandin F_{2α}
- o Urinary 11-Dehydrothromboxane B₂
- o Blood Soluble Intercellular Adhesion Molecule-1 (sICAM-1)
- o Urinary 4-(methylnitrosamino)-1-(3-pyridyl)-1-butanol and its glucuronides (total NNAL)
- o Carboxyhemoglobin (COHb)

^b Baseline of the 12-week ALCS-RA-16-06-EV study (CA20130), Week 1, will be used.

^c Subjects who exclusively use e-vapor products and have exhaled carbon monoxide (eCO) measurements ≤ 8 ppm from Week 6 (of the 12-week ALCS-RA-16-06-EV study) through Week 24 (EOS) and urine N-nitrosonornicotine (NNN) levels from

Week 6 (of the 12-week ALCS-RA-16-06-EV study) through Week 24 (EOS) consistent with switching to an e-vapor product.

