2.1.2 Secondary Objectives

The secondary objectives are to:

- Assess changes in forced expiratory volume in the first second (FEV₁), forced vital capacity (FVC) and FEV₁/FVC ratios from Screening/Visit 2 of the 12-week ALCS-RA-16-06-EV study (CA20130) to Week 18 and to Week 24 (EOS) between the Test and Control groups.
- Compare changes in selected biomarkers (same as those in the primary objective) from Baseline to Week 18 between Test and Control groups.
- Determine the number of cigarettes smoked (Test and Control groups) from Baseline through Week 24 (EOS).
- Assess changes in the amount of test e-vapor product use (Test groups only) from Baseline through Week 24 (EOS).
- Assess adherence to protocol by comparing changes from Baseline through Week 24 (EOS) within the Test groups for eCO and urinary NNN.

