At Visits 2 and 4 (Week 15 and Week 21, respectively), subjects will return to the study site with all of their used and unused cartridges, which will be counted. Vital signs will be taken and medical history and symptom-driven physical examination will be performed. Compliance with daily tobacco use reporting will be discussed and eCO will be measured; use of non-test product and/or eCO measurements > 5 ppm will prompt counseling by clinic staff on the tobacco and nicotine restrictions and, for measurements > 8 ppm, potential for removal from the study. Test Product for the following 3 weeks and a urine collection container will be dispensed. Subjects will receive reminder calls regarding their following clinic visits and need to collect the first void urine prior to returning to the study site (Visits 3 and 5).

[figure not shown]
At Visit 3 (Week 18), procedures will be as described for Visits 2 and 4 (Weeks 15 and 21, respectively), with the addition of spirometry, questionnaires, and collection of urine and blood for Week 18 biomarkers and future biomarker assessments. A urine collection container will not be dispensed at Visit 3

At Visit 5 (Week 24), subjects will return to the study site with all of their used and unused cartridges (which will be counted), blood and urine samples will be collected for Week 24 biomarker assessments, questionnaires will be completed, and subjects will undergo EOS procedures and be discharged from the study.

All subjects will report their cigarettes per day (Control and Test groups) and Test product use (Test groups only) daily using a SMS, i.e., text message, based system (Med-Quest). The self-reported cigarettes per day (CPD), use of other tobacco products, and measurements of eCO and NNN taken during the in-clinic visits will be used to monitor subject compliance with exclusive use of the Test products. All subjects will return to the study sites for four visits at Weeks 15, 18, 21, and 24.

Throughout this SAP, Screening refers to Visit 1 and/or Visit 2 of the 12-week ALCS-RA-16-06-EV study (CA20130), and study weeks are relative to Week 1 (Visit 3) of the 12-week ALCS-RA-16-06-EV study. Baseline values reported on Day 1 (Week 1) or at Screening (for spirometry only) of the 12-week ALCS-RA-16-06-EV study (CA20130) will be used, except for product use. Baselines for product use will be defined in the product use sections.

The overall design of the study is shown below.

BOE: Biomarker of Exposure

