4. ANALYSIS POPULATIONS

The Clinical Safety Population (CSP):

The CSP will consist of all subjects who are enrolled into this study and record at least one use of study products (i.e., conventional cigarettes or test e-vapor products) after Week 12.

The Modified Intent-to-Treat (mITT) Population:

The mITT population includes those subjects in the CSP population for which there is a baseline for a primary biomarker and at least one post-baseline biomarker measure for the primary biomarker after Week 12.

The Per-Protocol (PP) Population:

The PP population will be a subset of the mITT Population, which is comprised of subjects who completed the study without any major protocol violations, which are defined as:

- Control group: subjects who quit cigarette smoking (either by self report or NNN criteria of $\geq 80\%$ reduction in NNN from baseline at Visit 3 or 5).
- Test groups: subjects who self-report use of $> 10\%$ of baseline CPD over the course of the study*, subjects with an eCO > 8 ppm at any one visit in Visits 2 - 5, or subjects whose NNN levels are consistent with smoking cigarettes (ie, $< 80\%$ reduction in NNN from baseline) at Visit 3 or 5, and subjects who used ≤ 2 cartridges per week during any given week from Weeks 13 to 24.

*Baseline is defined as the CPD reported at Screening (Visit 2) of the 12-week ALCS-RA-16-06-EV study (CA20130), and the course of the study (post baseline) is defined as the average number of cigarettes smoked from Day 1, Week 1 of ALCS-RA-16-06-EV through the end of Week 24.

The CSP and PP populations will be used for the analyses of subject demographics, baseline characteristics and tobacco product use.

The mITT and PP populations will be used for the analyses of the primary endpoint. All other endpoints (excluding demographics, baseline characteristics, and safety data) will be analyzed based on the mITT population concept defined for each endpoint that includes subjects who has a baseline value and at least one post-baseline value. A PP population will be applied to the spirometry dataset using the criteria listed above.

The CSP will be used for the analyses of AEs, vital signs, clinical laboratory findings and other study safety related variables.

If it is determined that a subject was pregnant during the study, all of the pregnant subject's safety and biomarker data will be reported, but will be excluded from the biomarker summarization and statistical analyses.

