6.1.2 Blood Biomarkers of Exposure and Biomarkers of Potential harm

6.1.2.1 Blood BOE and BOPH Sample Collection

Blood samples (approximately 4 mL each) will be collected via direct venipuncture for WBC count, sICAM-1 concentration, HDL-C concentration, and COHb saturation analysis at Visits 3 and 5.

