 Test 2 Group = e-Vapor Product XIMB
 Control Group = Continue smoking lit-end conventional cigarette

Program: /CAXXXXX/sas_prg/pksas/PROGRAMNAME.SAS DDMMYYYY HH:MM

Note: Tables 14.2.2.4.2, 14.2.2.4.3, and 14.2.2.4.3, (Creatinine-adjusted NNN, absolute change from baseline in creatinine-adjusted NNN, and percent change from baseline in creatinine adjusted NNN) have a similar format as Tables 14.2.1.1.1, 14.2.1.1.2.1, and 14.2.1.1.3.1 above.

Table 14.2.2.4.3 Frequency of eCO and Urine NNN by Study Group and Visit

Page 1 of X

| Group | Visit | N | eCO (ppm) | | | Urine NNN % reduction* | |
|---------|----------|----|--------------|--------------|-------------|------------------------|---------------|
| | | | ≤ 5 n (%) | 5–8 n (%) | >8 n (%) | <80% n (%) | ≥80% n (%) |
| Test 1 | Baseline | XX | XX (XX) | XX (XX) | XX (XX) | ND | ND |
| | 2 | XX | XX (XX) | XX (XX) | XX (XX) | ND | ND |
| | 3 | XX | XX (XX) | XX (XX) | XX (XX) | XX (XX) | XX (XX) |
| | 4 | XX | XX (XX) | XX (XX) | XX (XX) | ND | ND |
| | 5 | XX | XX (XX) | XX (XX) | XX (XX) | XX (XX) | XX (XX) |
| Test 2 | Baseline | XX | XX (XX) | XX (XX) | XX (XX) | ND | ND |
| | 2 | XX | XX (XX) | XX (XX) | XX (XX) | ND | ND |
| | 3 | XX | XX (XX) | XX (XX) | XX (XX) | XX (XX) | XX (XX) |
| | 4 | XX | XX (XX) | XX (XX) | XX (XX) | ND | ND |
| | 5 | XX | XX (XX) | XX (XX) | XX (XX) | XX (XX) | XX (XX) |
| Control | Baseline | XX | XX (XX) | XX (XX) | XX (XX) | ND | ND |
| | 2 | XX | XX (XX) | XX (XX) | XX (XX) | ND | ND |
| | 3 | XX | XX (XX) | XX (XX) | XX (XX) | XX (XX) | XX (XX) |
| | 4 | XX | XX (XX) | XX (XX) | XX (XX) | ND | ND |
| | 5 | XX | XX (XX) | XX (XX) | XX (XX) | XX (XX) | XX (XX) |

Note: *Reduction from Baseline

ND = Not done

Baseline = Day 1 (Week 1) of the 12-week ALCS-RA-16-06-EV study (CA20130)

Visit 3 = Week 18 (Day 126 ± 3)

Visit 5 = Week 24 (Day 168 ± 3)

Test 1 Group = e-Vapor Product XLCB

Test 2 Group = e-Vapor Product XIMB

Control Group = Continue smoking lit-end conventional cigarette

Program: /CAXXXX/ECR/sas_prg/pksas/PROGRAMNAME.sas DDMMYYYY HH:MM

Note: Tables 14.2.3.1.1 and 14.2.3.1.2 will be in the following format:

Page 1 of X
 Table 14.2.3.1.1 Summary of Pulmonary Function Parameters by Study Group and Visit (All Subjects*)

| Parameter | Visit | Group | | |
|----------------------|-----------------|-----------|--------|---------|
| | | Test 1 | Test 2 | Control |
| Measured FEV1 (L) | Baseline | n | X | X |
| | | n missing | X | X |
| | | Mean | X.X | X.X |

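### Later-visit compliance percentages for the Test groups can be overstated, because subjects removed for eCO > 8 ppm leave the denominator and no rule carries their failure forward

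*SAP*

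**What the plan says.** The secondary objective (SAP Section 2.1.2) is: "Assess adherence to protocol by comparing changes from Baseline through Week 24 (EOS) within the Test groups for eCO and urinary NNN". Section 6.2.5 serves it with frequency tables of eCO (≤ 5, > 5 to ≤ 8, > 8 ppm) and NNN (< 80% or ≥ 80% reduction) in each study group.

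The two markers have different analysis sets. For NNN, Section 6.2.5 states: "Analysis of NNN will be performed on the mITT population". For the rest, including eCO, it states: "Other product use and compliance variables will be summarized using available data".

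The output is titled "Frequency of eCO and Urine NNN by Study Group and Visit". It is listed in Section 8 as Table 14.2.2.4.5, while its shell in Section 10 carries the number 14.2.2.4.3. The shell has one N per group and visit, shared by eCO and NNN. It names no population and has no row or column for missing or removed subjects.

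Section 3 provides for counselling after high eCO readings and, "for measurements > 8 ppm, potential for removal from the study". Footnote c to the primary objective (Section 2.1.1) defines complete switching by sustained criteria: "Subjects who exclusively use e-vapor products and have exhaled carbon monoxide (eCO) measurements ≤ 8 ppm from Week 6" of the parent study through Week 24, together with NNN levels consistent with switching.

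**The concern.** The outcome being tabulated can cause its own later missingness. A Test subject with eCO above 8 ppm at Week 15 counts as a failure in the Week 15 row. If that subject is removed, the Week 18, 21 and 24 rows contain neither the failure nor the subject. The Week 24 percentage then describes those who were not removed and still attend, and it can rise through attrition alone. The error favours the Test groups on a stated secondary objective.

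A second gap needs no removals. Percentages shown one visit at a time cannot tell a reader how many subjects stayed compliant throughout, which is how footnote c frames switching.

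**Working it through.** The SAP states no adherence rate and no removal count, so there is no figure to reproduce. The check is direct arithmetic on assumed inputs.

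**Inputs.** Enrolled Test subjects (Section 3): 50 in Test 1 and 48 in Test 2, so N = 50 + 48 = 98. Assumed: r = subjects removed for eCO > 8 ppm before Week 24, from 0 to 20; share of those remaining with eCO > 8 ppm at Week 24, from 0% to 20%, with 10% shown below. c = remaining subjects with eCO ≤ 8 ppm, rounded to whole subjects.

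**Formulas.** Available-data rate = c/(N − r). Rate with removed subjects counted as non-adherent = c/N. Difference = [c/(N − r)] × (r/N).

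| r | N − r | c | c/(N − r) | c/N | Difference (points) |
|---|---|---|---|---|---|
| 0 | 98 | 88 | 89.8% | 89.8% | 0.0 |
| 2 | 96 | 86 | 89.6% | 87.8% | 1.8 |
| 5 | 93 | 84 | 90.3% | 85.7% | 4.6 |
| 10 | 88 | 79 | 89.8% | 80.6% | 9.2 |
| 20 | 78 | 70 | 89.7% | 71.4% | 18.3 |

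Over the whole assumed grid the difference runs from 0 to 20.4 points; the maximum is at r = 20 with nobody remaining above 8 ppm. The actual table is by group, where one removal is 1/50 = 2.0% of Test 1 or 1/48 = 2.1% of Test 2, multiplied by the available-data rate.

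**Departures unrelated to smoking.** If 10 of 98 leave and 9 of them would have been compliant, the rate over all enrolled is (79 + 9)/98 = 89.8%, the same as the available-data rate of 79/88 = 89.8%. The overstatement comes from departures linked to failure.

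**NNN.** The mITT set (Section 4) requires "at least one post-baseline biomarker measure for the primary biomarker after Week 12". The scheduled biomarker samples that could meet this come late: Section 6.1.2.1 sets blood draws for "COHb saturation analysis at Visits 3 and 5", and Sections 6.1.1.1 and 6.1.3.1 put urine collection at the same two visits. A subject removed at Visit 2 is therefore outside mITT unless sampled at termination. A subject removed at Visit 3 after sampling, or at Visit 4, is in mITT but has no Visit 5 NNN. The carry-forward analysis in Section 6.3.5.2 does not fill it, because Section 6.3.5.1 limits the sensitivity analyses to the primary endpoints and NNN is not one of them.

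**Sustained adherence.** Suppose 5 of 50 subjects exceed 8 ppm at each of Visits 2 to 5 and nobody is removed. Every visit shows 45/50 = 90%. If the same 5 fail each time, 45/50 = 90% stayed compliant. If different subjects fail each time, 4 × 5 = 20 failed at some visit and 30/50 = 60% stayed compliant. The by-visit table is identical in both cases.

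**The case against.** The strongest reply is that the by-visit table delivers what was specified. The objective and the outcome variables in Section 2.2 concern eCO and NNN at stated visits, and the SAP defines no switching rate. That stands. A reader might take the Week 24 cell as the proportion who stayed switched, but the SAP does not call it that.

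It can also be said that attrition is visible elsewhere. The reading that triggers removal is counted at its own visit. The shell prints N by visit, the eCO summary (Table 14.2.2.4.1) has a count of missing values, Table 14.1.1 gives reasons for discontinuation, and Appendix 16.2.5.5 lists each subject's eCO category. This also stands, and it rules out saying that the SAP hides the problem. None of these outputs, however, links departures to compliance status in the compliance table itself.

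The per-protocol count in Table 14.1.1 comes closest to a sustained figure. Section 4 excludes Test subjects with eCO above 8 ppm at any of Visits 2 to 5, or with an NNN reduction below 80% at Visit 3 or 5. But it also excludes non-completers and applies cigarette-use and cartridge-use criteria, so the count answers a narrower question and discloses eCO and NNN adherence only in part.

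Finally, enrolment was limited to subjects compliant in the parent study, so removals may be few. The documents give no number either way.

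**Conclusion.** The concern holds in a limited form: compliance percentages at later visits can be overstated for the Test groups. The amount is zero with no removals. With 10% of the remaining subjects above 8 ppm, it is 1.8 points at 2 removals of 98 and 18.3 points at 20. The removal count and the 10% are assumptions, and the comparison counts every subject removed for eCO > 8 ppm as non-adherent afterwards.

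Three stronger readings are not supported. A reader might infer that the rate is inflated as a matter of fact, but removal is only a possibility. A reader might infer that both markers are summarised on available data only, but Section 6.2.5 assigns NNN to mITT; the weakness there is that mITT does not supply a missing Visit 5 value. A reader might treat every departure as a return to smoking and quote the resulting gap as the overstatement, but unrelated withdrawals need not inflate the rate.

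**What to change.** In Section 6.2.5 and the eCO/NNN frequency table:

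1. Keep the available-data percentages, and state the population and denominator separately for eCO and NNN.
2. For the Test groups, add a percentage over all enrolled subjects (50 and 48). Count subjects removed for eCO > 8 ppm as non-adherent at later visits, and show other missing or withdrawn subjects in a separate row.
3. Add one subject-level row per Test group for sustained adherence over Visits 2 to 5, using the thresholds already in Section 4: eCO ≤ 8 ppm at every visit and NNN reduction ≥ 80% at Visits 3 and 5, with missing counted as not met. Label it as covering the extension period only, not the full Week 6 to Week 24 definition in footnote c.

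This row needs eCO at Visit 2. Section 6.1.3.1 lists eCO at Visits 3, 4 and 5 only, while Sections 3, 4 and 6.1.3.2 and the Table 14.2.2.4.1 shell also use Visit 2. These sections need reconciling, as does the table number.

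The cost is SAP wording and one reshaped table, with no new data. The adherence figure may look less favourable, and the sustained row is conservative for subjects who leave for reasons unrelated to smoking.

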6.2.6 Questionnaires

The responses and the following factor scores from the QGEN and TQOLIT will be presented and listed by subject and study visit:

- QGEN Physical Health General Score
- QGEN Emotional Health General Score
- QGEN estimated Physical Component Summary
- QGEN estimated Mental Component Summary
- TQOLIT Physical Functioning Supplemental
- TQOLIT General Health-Confidence
- TQOLIT Smoking Symptoms
- TQOLIT Smoking or Vaping Impact

The mCEQ will be considered as a 7-point scale and treated as a continuous variable. The responses from mCEQ-C or mCEQ-E will be listed as individual responses and as following factor scores¹ by subject and study visit:

- Smoking satisfaction: average of the response scores from questions 1, 2, and 12;
- Psychological reward: average of the response scores from questions 4 to 8;
- Aversion: average of the response scores from questions 9 and 10;
- Enjoyment of sensation: response score from question 3;
- Craving Reduction: response score from question 11.

Descriptive statistics (n, n missing, mean, SD, CV%, SEM, minimum, Q1, median, Q3, maximum, and 95% CI) of each of the response score and factor score will be provided by study group and study visit.

The responses from Cough Questionnaire (Baseline*, Visits 3 and 5) and Reasons of Use/Not-Use Test Product Questionnaire (Visit 5) will be listed by subject and study

¹ Cappelleri et al. 2007. Confirmatory factor analysis and reliability of the modified cigarette evaluation questionnaire. Addictive Behaviors. (32)912-923

visit. The frequency (n, %) of responses to Questions I and III through X will be summarized by study group. The responses to Question II will be summarized by study group using the same descriptive statistics as for the above questionnaires.

The above questionnaire analyses will be conducted using the dataset of subjects with a baseline and at least one post-baseline response for each individual question, with the exception of Reasons of Use/Not-Use, which will be summarized using available data.

*Baseline values reported on Day 1 (Week 1) of the 12-week ALCS-RA-16-06-EV study (CA20130) will be used.

